9.3 Summary of findings from clinical studies

The development program of rhC1INH comprises a total of 714 exposures to rhC1INH in 190 subjects. As can be seen from the table below, it not only concerns symptomatic patients for the treatment of acute attacks, but also healthy volunteers and asymptomatic patients. Each of these studies is separately discussed in this paragraph.

| Study | Study Population | Number of Subjects ^a | Number of Administrations |
|--------------------------|---------------------------------|---------------------------------|---------------------------|
| 1202/1203 | Symptomatic HAE patients | 14 | 21 |
| 1205 RCT | Symptomatic HAE patients | 25 | 25 |
| 1205 OLE | Symptomatic HAE patients | 62 | 168 |
| 1304 RCT | Symptomatic HAE patients | 16 | 16 |
| 1304 OLE | Symptomatic HAE patients | 57 | 194 |
| Subtotal | Symptomatic HAE patients | 155 | 424 |
| 1101 | Asymptomatic HAE patients | 12 | 24 |
| 1106 | Healthy volunteer subjects | 14 | 59 |
| 1207 | Asymptomatic HAE patients | 25 | 207 |
| Total all studies | All populations | 190 | 714 |

^a Because some subjects participated in more than one study, the total number of subjects is smaller than the number reached by adding the number of subjects in each of the individual studies.

Study C1 1101-01

In Study C1 1101-01, administration of escalating doses of rhC1INH (6.25 to 100 U/kg) to 12 asymptomatic HAE patients resulted in dose-dependent increases of C1INH activity. Doses of rhC1INH of 50 U/kg and 100 U/kg were found to restore C1INH activity to normal levels (0.7 -1.3 U/mL), while doses of 25 U/kg and lower did not. After administration of 50 U/kg rhC1INH, a C_{max} of 1.36 U/mL is observed. Levels remain above 0.7 U/mL for approximately 2 hours and then subside to baseline levels in approximately 4 hours. rhC1INH was shown to be pharmacodynamically active in HAE patients through a dose-dependent decrease in the formation of C4b/c, the activation cleavage product of plasma complement C4. Doses of 100 U/kg and 50 U/kg increased mean normalized levels of C4 relative to baseline, and cleavage of C4 resumed once C1INH activity levels fell below 0.7 U/mL. Doses of rhC1INH of 25 U/kg or lower only resulted in a temporary, minimal elevation of C4 levels relative to baseline.

Studies C1 1202-01 and C1 1203-01

Exploratory efficacy Studies C1 1202-01 and C1 1203-01 were undertaken in 14 symptomatic HAE patients, treated for 21 acute angioedema attacks.

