The treatment appeared safe and well-tolerated. No clinically significant AEs, changes in vital signs, safety laboratory parameters or antibody responses to C1INH or rabbit milk protein were observed. The PK findings from Study C1 1101-01 were confirmed in HAE patients treated with rhC1INH for an acute angioedema attack. Both patients and physicians evaluated treatment with rhC1INH as favorable compared to previous untreated attacks. The median time to the beginning of relief was 30 and 60 minutes, as reported by physicians and patients, respectively. The median time to minimal symptoms was 4 hours. All treated attacks resolved completely and no relapses occurred. No difference in response was observed on first and repeated treatments.

Study C1 1106-02

In Study C1 1106-02, fourteen healthy volunteers were enrolled to receive rhC1INH at 100 U/kg on five occasions with intervals of approximately 3 weeks between doses. Serial PK sampling was performed following the first, third and fifth administrations of rhC1INH. After administration of rhC1INH the levels of C1INH activity peaked at median times of about 20-30 minutes and thereafter declined to endogenous levels in about 8 to 12 hours. No difference in PK profiles was observed following the 1st, 3rd, and 5th administrations of rhC1INH.

One anaphylactic reaction occurred in an adult female participating in this study on first exposure to rhC1INH. This patient had a clinical history of rabbit allergy (not disclosed during the study pre-consent screening procedure). The patient was also subsequently found to have a clinically significant IgE antibody level against rabbit epithelium (dander) allergens.

No clinically significant changes in hematology, biochemistry, urinalysis, coagulation, vital signs or ECG parameters or physical examinations were noted in this study.

Study C1 1207

In Study C1 1207, an open-label exploratory phase II study, the safety and prophylactic effect of weekly administrations of rhC1INH was studied in asymptomatic HAE patients. Twenty-five patients were enrolled and treated with rhC1INH at 8 weekly administrations of 50 U/kg and followed up for 42 days after the last administration.

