Results of the primary endpoint, time to beginning of relief, showed a sustained efficacy of rhC1INH in repeated treatments for attacks 1 to 5 of 63, 61, 37, 51 and 67 minutes (Median time to beginning of relief using the overall VAS score). The 95% confidence intervals of the repeated attacks are overlapping (30-124 min).

Immunology testing revealed the presence of confirmed anti-rhC1INH antibodies in 2/62 patients at any time point during the study, but no neutralizing antibodies. Confirmed antibodies against Host Related Impurities were found in 2/62 patients at any time point during the study without associated clinical symptoms.

Thirty-nine patients (63%) reported at least one treatment emergent adverse event, most of them mild to moderate in severity; 8 TEAEs were possibly related to treatment according to the investigator's opinion. Seven adverse events were considered severe in intensity, none of them assessed by the investigator as treatment related. Twenty-two SAEs were reported in 10 patients. Thirteen SAEs were HAE attacks in 7 patients. All SAEs resolved and none was related to treatment in the investigator's opinion except for a "hypersensitivity reaction" which was considered possibly related to treatment. Laboratory data suggest that the event was not an IgE-mediated reaction.

Repeated treatments with rhC1INH showed continued efficacy and appeared generally safe and well tolerated.

Adolescent patients treated in the open label extension studies

In the open label extension studies mentioned above, enrolment of adolescent patients was allowed, and this subset of data was separately evaluated. A total of 16 patients have been exposed to rhC1INH for a total of 50 treatments of an acute HAE attack, ranging from 14 to 17 years of age at the time of treatment; 8 patients have been exposed to rhC1INH for at least three HAE attacks, 2 patients even up to 7 HAE attacks.

Due to the different dosing strategies, there was a range in treatment doses, varying from 25 U/kg to 100 U/kg. As for the adult population, PK-data in adolescents indicated that a dose of 50 U/kg will restore deficient levels of C1INH activity into the normal range (70% to 130%).

Safety of Ruconest in 2-13 year old HAE patients

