10.6 Subject and Study Stopping Rules

Subject stopping rule

A subject who experiences a treatment-emergent anaphylactic/anaphylactoid reaction or a confirmed adverse event of special interest, as specified in section 11.2. will be withdrawn and the case will be reviewed, discussed with the treating investigator, and further evaluated as required.

Study stopping rule

Further enrollment into the study, and further Ruconest administration in all subjects, will be temporarily halted pending a review of the data by the Data Safety Committee if two patients experience a treatment-emergent anaphylactic/anaphylactoid reaction or a confirmed adverse event of special interest, as specified in section 11.2. Only after review of the relevant data by this committee, the study may be reinitiated.

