11.2 Adverse Events of Special Interest

Adverse Events of Special Interest (AEOSI) are AEs that do not meet any criteria for an SAE but are nonetheless of particular interest in the context of this study. AEOSIs will be collected for all patients during the study period. Although these are non-serious events, the Investigator will be asked to provide detailed initial information and follow up to Pharming (see contact details in section 11.1.5) by using Pharming's CRF and SAE Report Form. Pharming Pharmacovigilance will periodically review the AE data including all AEOSIs.

The list of AEOSI with reporting timelines are presented below:

| Adverse Events of Special Interest | Reporting timelines to Pharming PV |
|------------------------------------------------------------------------------------------------------|------------------------------------|
| Type I hypersensitivity reaction due to pre-existing IgE antibodies against rabbit antigens | 24 hrs |
| Type I hypersensitivity reaction due to cross reaction with IgE antibodies against cow milk antigens | 24 hrs |
| Type I hypersensitivity reaction due to the formation of IgE antibodies against rabbit antigens | 24 hrs |
| Type III hypersensitivity reaction due to the formation of antibodies against Ruconest | 24 hrs |
| Induction of acquired angioedema due to the formation of anti-C1 inhibitor antibodies | 24 hrs |
| Thromboembolic complications | 24 hrs |

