Adverse Events of Special Interest (AEOSI) are AEs that do not meet any criteria for an SAE but are nonetheless of particular interest in the context of this study, as listed below:

- Type I hypersensitivity reaction due to pre-existing IgE antibodies against rabbit antigens.

- Type I hypersensitivity reaction due to cross reaction with IgE antibodies against cow milk antigens.
- Type I hypersensitivity reaction due to the formation of IgE antibodies against rabbit antigens.
- Type III hypersensitivity reaction due to the formation of antibodies against Ruconest.
- Induction of acquired angioedema due to the formation of anti-C1 inhibitor antibodies.
- Thromboembolic complications.

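### The AEOSI definition excludes serious events, so a serious listed event other than an anaphylactic/anaphylactoid reaction falls outside the Protocol 10.6 rules, and every serious listed event falls outside SAP Table 14.3.2.3

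*SAP*

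**What the plan says.** Protocol 11.2 and SAP 4.2.2.1 share one definition: "Adverse Events of Special Interest (AEOSI) are AEs that do not meet any criteria for an SAE but are nonetheless of particular interest". Six event types follow: three kinds of type I hypersensitivity, type III hypersensitivity to Ruconest, induced acquired angioedema, and thromboembolic complications. Protocol 11.2 repeats the limit when it sets out reporting: "Although these are non-serious events, the Investigator will be asked to provide detailed initial information and follow up to Pharming".

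Protocol 10.6 then uses the category twice. Under the subject rule, one limb covers anaphylaxis and similar reactions, and the other extends withdrawal to AEOSIs: "or a confirmed adverse event of special interest, as specified in section 11.2. will be withdrawn". The study rule has the same two limbs and applies "if two patients experience a treatment-emergent anaphylactic/anaphylactoid reaction or a confirmed adverse event of special interest, as specified in section 11.2". Its consequence is a pause, in which enrolment and dosing "will be temporarily halted pending a review of the data by the Data Safety Committee". Neither rule mentions SAEs.

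SAP 6.8.2 and Attachment 1 plan one AEOSI output, Table 14.3.2.3. The SAP gives no way to select its events other than the 4.2.2.1 definition. Seriousness is taken from the CRF question (SAP 4.2.2.1).

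**The concern.** Excluding serious events makes sense for a reporting category, because SAEs already go to the sponsor within 24 hours under Protocol 11.1.5. It does not suit a stopping rule or a summary table. A thromboembolic complication assessed as non-serious requires withdrawal and counts toward the halt. The same complication leading to hospitalisation does neither, so the rule weakens as severity rises.

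Safety is the primary objective, and Protocol 11.5 provides no formal independent monitoring board. What is at stake is the automatic part of the safeguard and a complete AEOSI count.

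**Working it through.** **Tracing the definition by event type.** For an event that is treatment-emergent and already serious when confirmed:

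| Serious listed event | AEOSI as defined? | Triggers 10.6? | In Table 14.3.2.3? | Re-dosing barred by Protocol 7.3? |
|---|---|---|---|---|
| Type I, anaphylactic/anaphylactoid | No | Yes, by its own limb | No | Yes |
| Type I, other | No | No | No | Yes |
| Induced acquired angioedema | No | No | No | Yes |
| Type III | No | No | No | Arguable |
| Thromboembolism | No | No | No | No |

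The last column rests on the treatment exclusions in Protocol 7.3. Any change since screening that would meet a screening exclusion blocks treatment. Those exclusions cover allergy to rabbits or rabbit-derived products (rhC1INH is named), a positive anti-rabbit IgE test, and acquired C1INH deficiency. None depends on seriousness.

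**Table.** With 20 patients in the Safety Set, one serious thromboembolic TEAE gives 1/20 = 5% in Table 14.3.2.1 and 0/20 in Table 14.3.2.3.

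**Two-patient halt.** The plan states no operating characteristics for the rule, so there is no figure to reproduce. Inputs:
- n = 20, the minimum number treated (Protocol 7.5).
- p, the per-patient risk of a listed event not classed as anaphylactic/anaphylactoid: an assumption. Protocol 9.3 gives the base: "The development program of rhC1INH comprises a total of 714 exposures to rhC1INH in 190 subjects". It describes no thromboembolic event. It describes one serious hypersensitivity reaction, in the 1205 open-label extension, "which was considered possibly related to treatment. Laboratory data suggest that the event was not an IgE-mediated reaction". Whether that reaction would be a listed type is not stated, so p is anchored at 0 to 1/190.
- s, the share of such events that are serious when confirmed: an assumption.

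The risk that counts under the current wording is q = p(1 − s), and

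P(at least 2 of 20) = 1 − (1 − q)^20 − 20q(1 − q)^19.

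Upper anchors:
- One-sided 95% bound for 0/190: 1 − 0.05^(1/190) = 1.56%.
- Exact upper 95% limit for 1/190: the 0.975 quantile of Beta(2, 189) = 2.90%.

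Worked for p = 1/190 with all events counted: 1 − 0.89984 − 0.09522 = 0.0049. For p = 2.90%: 1 − 0.55541 − 0.33146 = 0.1131.

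| p | All listed events counted | As written, s = 50% | As written, s = 100% |
|---|---|---|---|
| 0.53% (1/190) | 0.5% | 0.1% | 0% |
| 1.56% | 3.9% | 1.1% | 0% |
| 2.90% | 11.3% | 3.4% | 0% |

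The s = 100% column is zero by construction. Within the anchored range the loss is at most 0.5 percentage points. At the upper limit it is 11.3 − 3.4 = 7.9 points if half the events are serious, and 11.3 points if all are.

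Anaphylaxis is left out because it counts in any case. The halt pools both limbs, however, so a serious listed event could also be the second case after an anaphylaxis. Giving anaphylaxis its own 1/190, with p = 1/190 and s = 100%, the chance with all events counted is taken at q = 2/190: 1 − 0.80925 − 0.17218 = 1.9%. As written it is 0.5%, a loss of 1.4 points, which is still small.

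**The case against.** **The reference to 11.2 may mean only the list.** The list has no seriousness column, and this is probably what was intended. But 11.2 states the non-serious limit twice, and a stopping rule should not depend on readers setting aside a condition in the section it cites. The intent stands as plausible; the wording remains wrong.

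**Mandatory protection already exists at subject level.** This largely stands. Protocol 7.3 bars further dosing after most listed types. Protocol 6 allows repeat treatment only while anti-rabbit IgE stays negative, and Protocol 10.2.1.3 requires that test after events suggesting hypersensitivity. The bar is not formally withdrawal, but it likewise means no more Ruconest. A reader might infer that a child could be re-dosed after any serious listed event unless someone used discretion; 7.3 does not support that.

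**Serious anaphylaxis still counts.** This stands. A reader might infer that all serious listed events escape 10.6, but anaphylactic/anaphylactoid reactions are a separate limb with no seriousness limit. The programme's known case is of that kind: "One anaphylactic reaction occurred in an adult female participating in this study on first exposure to rhC1INH".

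**Nothing is hidden.** This also stands. Serious listed events appear in Tables 14.3.1.2.1 and 14.3.2.1 and Listing 16.2.7.2. The internal committee reviews data regularly (11.5), the investigator can stop treatment (10.3), and either party can end the study (10.7). With about 20 patients the AEOSI count can be recovered by hand, but Table 14.3.2.3 would still be incomplete under its own title.

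**Conclusion.** Wrong as written; minor. On the literal text, four kinds of serious listed event (thromboembolism, type III hypersensitivity, induced acquired angioedema, non-anaphylactic type I reactions) neither count toward the two-patient halt nor trigger withdrawal under 10.6. All serious listed events, anaphylaxis included, drop out of Table 14.3.2.3. The gap concerns events already serious when confirmed; nothing in 10.6 removes a confirmed AEOSI that later worsens.

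In practice the subject-level gap is mainly thromboembolism, and arguably type III reactions. The effect on the halt is at most about 0.5 points for p between 0 and 1/190, and about 11 points only if p is at its upper 95% limit and every event is serious. Both p and s are assumptions. The 190 subjects include healthy volunteers and nobody under 14, so the paediatric risk could differ. A reader might infer that the halt is seriously disabled or that serious events go undetected; the documents support neither. The halt is also only a temporary pause for committee review.

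**What to change.** In Protocol 11.2 and SAP 4.2.2.1, define AEOSIs as the listed events *whether or not they meet SAE criteria*, and remove the clause in 11.2 that calls them non-serious. Protocol 10.6 then works without further change. The event list, the 24-hour timeline and the two-patient threshold stay as they are. Produce Table 14.3.2.3 with serious listed events included, and footnote that these also appear in Table 14.3.2.1 so that the two are not added together.

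No new data are needed, because SAEs are already collected and coded. In a running study the protocol change could count as a substantial amendment needing EC and CA approval (Protocol 14.5.1), since it touches a stopping rule. Here the SOP deviation form attached to the SAP states that the analysis is final. The live action is therefore to produce the completed table and describe the change in the CSR, as SAP 7.5 provides. The rule wording should be corrected if this protocol text is reused.

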Table 14.2.2.1.2	Functional C1INH (% of Normal) Cmax and AUC(0-3) Parameters	PK/PD Analysis Set	Unique
Table 14.2.2.2	C4 Concentrations Over Time	PK/PD	Unique

Table Number	Title	Analysis Set	Repeat
		Concentration Set	
Table 14.3.1.1	Summary of Adverse Events	Safety	Unique
Table 14.3.1.2.1	Incidence of Treatment-Emergent Adverse Events	Safety	Unique
Table 14.3.1.2.2	Incidence of Related Treatment-Emergent Adverse Events	Safety	Repeat of 14.3.1.2.1
Table 14.3.1.2.3	Incidence of Treatment-Emergent Adverse Events Commencing Within 24 Hours of the Completion of the Infusion of Study Drug Administration	Safety	Repeat of 14.3.1.2.1
Table 14.3.1.2.4	Incidence of Treatment-Emergent Adverse Events Commencing Within 28 Days of the Completion of the Infusion of Study Drug Administration	Safety	Repeat of 14.3.1.2.1
Table 14.3.1.2.5	Incidence of Treatment-Emergent Adverse Events by Strongest Relationship (Investigator's Judgment)	Safety	Unique
Table 14.3.1.2.6	Incidence of Treatment-Emergent Adverse Events by Maximum Severity (Investigator's Judgment)	Safety	Unique
Table 14.3.2.1	Incidence of Treatment-Emergent Serious Adverse Events	Safety	Unique
Table 14.3.2.2	Incidence of Treatment-Emergent Adverse Events Leading to Study Discontinuation	Safety	Repeat of 14.3.2.1
Table 14.3.2.3	Incidence of Treatment-Emergent Adverse Events of Special Interest	Safety	Repeat of 14.3.2.1
Table 14.3.4.1.1	Summary of Quantitative Laboratory Parameters	Safety	Unique
Table 14.3.4.1.2	Summary of Change in Quantitative Laboratory Parameters from Presentation of Attack to Day 28	Safety	Repeat of 14.3.4.1.1
Table 14.3.4.1.3	Summary of Quantitative Laboratory Parameter Classifications Based on Laboratory Reference Ranges	Safety	Unique
Table 14.3.4.1.4	Change in Status of Hematology Laboratory Parameters Based on Laboratory Reference Ranges from Presentation of Attack to Day 28	Safety	Unique
Table 14.3.4.1.5	Change in Status of Biochemistry Laboratory Parameters Based on Laboratory Reference Ranges from Presentation of Attack to Day 28	Safety	Unique
Table 14.3.4.1.6	Incidence of Clinically Significant Quantitative Laboratory Parameters	Safety	Unique
Table 14.3.4.1.7	Change in Status of Quantitative Laboratory Parameters According to Clinical Significance from Presentation of Attack to Day 28	Safety	Unique
Table 14.3.4.2.1	Summary of Exposure to Study Medication	Safety	Unique
Table 14.3.4.2.2	Total exposure to rhC1INH	Safety	Unique

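### Every hypersensitivity event of special interest is worded by an antibody cause, so a non-serious allergic reaction with no attributed antibody need not enter the special-interest table

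*SAP*

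**What the plan says.** SAP 4.2.2.1 and protocol 11.2 give the same six adverse events of special interest (AEOSI). Four are hypersensitivity reactions:

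- The first concerns rabbit IgE present before treatment: "Type I hypersensitivity reaction due to pre-existing IgE antibodies against rabbit antigens" (protocol 11.2, same item in the SAP).
- The second, in the SAP's words, concerns milk: "Type I hypersensitivity reaction due to cross reaction with IgE antibodies against cow milk antigens".
- The third covers rabbit IgE that arises during the study: "Type I hypersensitivity reaction due to the formation of IgE antibodies against rabbit antigens".
- The fourth is the only one outside Type I: "Type III hypersensitivity reaction due to the formation of antibodies against Ruconest".

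The other two are acquired angioedema induced by anti-C1 inhibitor antibodies, and thromboembolic complications. The SAP also restricts AEOSI to "AEs that do not meet any criteria for an SAE but are nonetheless of particular interest in the context of this study". SAP 6.8.2 and Attachment 1 (Table 14.3.2.3, Safety set) plan a table titled "Incidence of Treatment-Emergent Adverse Events of Special Interest".

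Protocol 9.4.1 names allergic reaction to host-related impurities as the only significant clinical risk so far, and protocol section 5 makes safety the primary objective. The stopping rules in protocol 10.6 count anaphylactic/anaphylactoid reactions separately from a confirmed AEOSI, without saying what makes an AEOSI confirmed.

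**The concern.** A clinician sees an allergic reaction; the list asks for an allergic reaction with a named immunological cause. A reaction with no IgE or other antibody attributed to it matches none of the four items, and no general item catches the remainder. The special-interest table is where a reader will look for hypersensitivity in children. If it shows none, the reader may conclude that there were no reactions, when the table supports only the narrower statement that none was attributed to a listed mechanism.

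The count also rests on a judgement that the plan does not describe. SAP 4.2.2.1 ties seriousness, relatedness, discontinuation and death to named answers on the case report form. For AEOSI it gives no form field, term list, evidence standard or responsible person.

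**Working it through.** The plan states no figure on this point, so there is none to reproduce. The check is a reading of the definitions, followed by arithmetic for scale.

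**Step 1: can an event be placed in the four items from the planned data?**

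- Coding (SAP 4.2.2.2) yields lowest level term, preferred term and system organ class. None of these fields records an antibody result.
- Rabbit-epithelium IgE is measured at screening, at Day 28 of each attack, yearly, and when an event suggests hypersensitivity (protocol 10.2.1.3). It can therefore inform the two rabbit items.
- Cow-milk IgE is measured once, at screening. No result at the time of an event is planned for the cow-milk item.
- Antibodies to rhC1INH and to host-related impurities are measured before each treatment and at Days 28 and 90. They can inform the Type III item.
- Known rabbit allergy or a positive rabbit IgE test excludes a patient (protocol 7.3), so the item on pre-existing rabbit IgE should rarely apply.

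A reaction with negative or absent antibody results has no row of its own.

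**Step 2: have reactions outside the Type I items been seen?** Protocol 9.3 says of the 1205 open-label extension: "All SAEs resolved and none was related to treatment in the investigator's opinion except for a" hypersensitivity reaction, rated possibly related. It adds: "Laboratory data suggest that the event was not an IgE-mediated reaction". So reactions that fit none of the three Type I items do occur. The protocol does not say whether a Type III mechanism was considered. It also does not give this patient's total dose: the study started at 50 U/kg and allowed a further 50 U/kg.

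**Step 3: where would such a reaction be shown?** SAP 6.8.2 plans tables of all treatment-emergent events, related events, events within 24 hours and within 28 days, and serious events, by system organ class and preferred term, plus full listings. It groups no hypersensitivity terms.

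**Step 4: what a zero would mean.** Take n = 20, the minimum number of treated patients (protocol 7.5). The exact 95% upper limit for 0/20 is 1 − 0.025^(1/20) = 16.8%. Clopper-Pearson intervals for other counts:

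| Reactions counted | Proportion | Exact 95% CI |
|---|---|---|
| 0/20 | 0% | 0 to 16.8% |
| 1/20 | 5.0% | 0.1% to 24.9% |
| 2/20 | 10.0% | 1.2% to 31.7% |

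**Step 5: how likely is at least one reaction?** The chance in 20 patients is 1 − (1 − p)^20. The documents give no rate for non-serious reactions without an attributed antibody, so p is an assumption.

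| Assumed p per patient | Chance of at least one in 20 |
|---|---|
| 1/190 = 0.5% (one such event described among all subjects in the programme) | 10% |
| 1/62 = 1.6% (1205 extension alone; exact 95% CI 0.04% to 8.7%) | 27.8% (0.8% to 83.7% across that CI) |
| 2% | 33% |
| 5% | 64% |
| 10% | 88% |

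The first two rows borrow a serious event, so they indicate scale only and do not estimate what the mechanism wording would miss.

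**The case against.** The strongest reply is that the list demands no proof. It says only that a reaction is due to a cause. Protocol 11.2 requires AEOSI reports within 24 hours, with follow-up, while the IgE and antibody samples go frozen to a central laboratory. Protocol 10.6 speaks of a confirmed AEOSI, which suggests that unconfirmed ones can exist, and a suspected hypersensitivity event itself triggers rabbit IgE testing. An investigator could therefore report a suspected Type I reaction as an AEOSI before any result arrives. This stands: a reader might infer that an antibody must be demonstrated and that such a reaction would be kept out, but the documents support only that it need not enter.

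A reader might also take the 1205 reaction as proof that the mechanism wording would exclude a similar case. It is not. That reaction was serious, so the non-serious clause removes it before mechanism is considered, and a Type III cause is not ruled out. Nor can one say that one of the two reactions described in protocol 9.3 fits the list and the other does not. The other, an anaphylactic reaction in a healthy volunteer with rabbit IgE, has no stated seriousness.

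Finally, a reader might infer that such reactions would disappear from the report. They would not. They would appear in the general tables and listings. Protocol 11.1.1 asks for a syndrome rather than separate symptoms where possible, anaphylactic/anaphylactoid reactions count towards the stopping rules whatever their mechanism, an internal committee reviews safety data, and some 20 patients can be read case by case. What this does not supply is a grouping fixed before the data are seen, or a special-interest table that answers the question its title raises.

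**Conclusion.** The point holds as a gap in definition and presentation. All four hypersensitivity items depend on an IgE or antibody cause, no general item exists, and no evidence standard or assigner is stated. Table 14.3.2.3, followed as written, can show 0/20 when non-serious reactions without an attributed antibody occurred. Each such reaction left out moves the proportion by 5 percentage points at n = 20, against an upper limit of 16.8% for a true zero.

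How often this would happen cannot be estimated from the documents. The rates tried give 10% to 88% for at least one reaction among 20 children, and all of them are assumptions for this purpose. The conclusion rests on the wording of the list and does not depend on those rates. It does not extend to the claim that reactions would go unreported, or that the 1205 reaction demonstrates the mechanism problem. The thromboembolic item is already free of mechanism and is not affected.

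**What to change.** In SAP 4.2.2.1 and Table 14.3.2.3:

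1. Add one mechanism-independent row: any treatment-emergent event, serious or not, in a named MedDRA hypersensitivity/anaphylactic reaction term list or standardised query, fixed to the coding version used. Keep HAE attacks out of it, as SAP 4.2.2 already reports attacks not treated with study medication separately.
2. Beneath it, show the four listed hypersensitivity mechanisms as sub-rows, each split into antibody shown, not shown and not tested, using the IgE and antibody results already collected. The cow-milk sub-row should say that only a screening result exists.
3. State who assigns AEOSI status and on what evidence.

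The sponsor should also reconcile the word confirmed in protocol 10.6 with the AEOSI list in 11.2, so that the two sections can be read together.

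The cost is a few lines of SAP text and one expanded table from data already coded and collected. The broad row will include some unrelated rashes, which the sub-rows and the relatedness table help to put in context. If the database is already locked, SAP 7.5 provides for the change to be described and justified in the clinical study report.
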